There were some suggestions to alter some of the wording within the information sheet. This included changing “you will” to “I need you to”. These changes were considered but not applied to reduce the likelihood of those reading feeling pressured into taking part. It was felt that “you will” conveys that there is structure to the study and may reduce the potential impact of demand characteristics by not applying too much emphasis onto each component. Moreover, depending on the sentence, the gunning-fog index of the text increased if the change was made, so this was avoided to ensure the information is simplified for accessibility and reducing the potential for distress when reading.

The eligibility questionnaire also received comments that it was easy to read and follow with a clear layout. Suggestions were made around reminding participants of why we are asking for specific personal details (e.g. NOK), so this has been made more explicit. There were some questions around whether the distress scale referred to post-stroke

distress or distress more generally, so this has also been made more explicit at the time the question is asked.

Video Call Instructions

PPI agreed these were clear and helpful and that it was well set out and logical. It was suggested that those unfamiliar with Teams may find it harder to follow, so we discussed alternative support that could be provided and agreed that talking to the participant via telephone as they are logging into a videocall can be provided prior to the study. It is hoped this will improve accessibility to the study.

Questionnaire Completion

PPI suggested the questionnaires should be conducted online rather than in paper format. Given the group therapy will be held online, they said it can likely be assumed the individual can use the basic functions of a device to do the questionnaire online. Additionally, it was agreed that paper surveys would increase burden placed on participants, whereby paper copies may get lost in the post or at home; they would need to be posted back, and not all stroke survivors are independent or able to get out easily; and surveys may not be completed at the right time. Therefore, online surveys were considered more practical and accessible to a wider population.

The platform chosen for the online survey (JISC) was one that allows participants to pause and return to. This means they do not need to complete the survey in one sitting. If they need breaks, this can be done easily, and they will not lose their answers.

To assess the potential for participant burden, PPI were asked to time how long it takes to complete each questionnaire, including recording any breaks they required. The 10-item questionnaire took one person 2 minutes and another 45 minutes. The 48-item questionnaire took both individuals 5-10 minutes to complete. This led to discussions around the impact of fatigue and distraction post-stroke so information at the start of every questionnaire has been added to encourage participants to complete at a time when they

are less tired/distracted and to seek support if required. My contact details have also been added to every page of the questionnaire so that if the individual requires support in completing the questionnaire, they can easily get in contact to discuss. It is hoped this will improve participant's experience of the study by making it easier to complete.

In regard to the feedback questionnaire, PPI found the questionnaire easy to understand and follow. It was suggested that greater emphasis on how the feedback will be used will improve the detail in responses. There was a suggestion that discussing the feedback with each participant may help to make it feel more personable and as though their individual comments are heard. We discussed the potential challenges of this, whereby some participants may not feel able to provide honest feedback if asked directly. The anonymity of the online questionnaire may help participants feel confident to provide critiques and suggestions for improvements. Therefore, it was agreed that giving participants the option to discuss the feedback with the research team directly was the next best solution. For this reason, this has been explicitly mentioned at the start of the questionnaire.

The final component PPI were asked to consider was how and when reminders to complete the questionnaire should be sent. It became clear that how people are reminded can come down to a matter of preference. However, PPI suggested that text messages are often more likely to be seen sooner than emails. For this reason, participants will be reminded via text (from a work phone) and via email. Links to the questionnaires will be provided in both messages, so that they can be accessed however the participant prefers. Discussions from PPI indicated that a reminder the day before and on the day would be most beneficial, given they must be completed within a certain timeframe. There were also suggestions around sending an additional reminder at 5pm on the day the questionnaire is due if the participant has not completed the questionnaire. To monitor who has completed the questionnaires, a box for participants to provide their initials has been added to the start of every questionnaire (except the feedback questionnaire). It is important the feedback questionnaire is anonymous, so participants feel able to disclose honest opinions on their

experiences of the therapy. In assigning initials to each questionnaire, it will also be possible to monitor psychological risk throughout the study to ensure participant safety.

Ethics

NHS Research Ethics Committee approval will be sought.

Informed Consent

All recruiting avenues will have access to the poster, information sheet, inclusion/exclusion criteria and consent forms, outlining the study's purpose, possible benefits/risks and handling of data. Documentation produced is informed by the Health Research Authority Guidelines (HRA, 2020).

Full written informed consent is required to access the eligibility questionnaire and individuals will be reminded of their right to withdraw at any time without explanation, as per BPS (2021) Ethical Guidelines. To improve accessibility, a consent to contact form is available (which can be signed by the individual themselves or by their clinician on their behalf following verbal consent to be contacted) and researchers can be contacted directly prior to consenting to participate.

Mental Capacity

All participants must have capacity to consent to participating. In accordance with the Mental Capacity Act 2005 (Department of Constitutional Affairs, 2007), capacity will be assumed unless proven otherwise. Appropriate steps will be taken to support individuals to make and communicate their decision. If lacking capacity to consent to participating, individuals will be excluded as this may impact their ability to engage.

During the study, capacity to consent to participating will be assumed when questionnaires are completed (NHS, 2021). Capacity will be monitored throughout the intervention and if no longer stands, participants will be removed from the study given the possibility of discussing personal and/or sensitive topics with people they do not know.

Confidentiality, Anonymity and Data Protection

All information collected will be on a needs-to-know basis, in accordance with GDPR safeguards (ICO, 2020). Reasons for collecting personal information will be provided when requested. Data will be stored in a password protected file saved on University of East Anglia's OneDrive which is only accessible by the research team. All personal and identifiable information will be stored separately to questionnaire responses.

Participants will not be pressured into sharing personal details. Information shared during the intervention will be of their own volition, not discussed with others and anonymised in the final report with pseudonyms and all identifiable information removed.

While participants will be reminded of confidentiality at the start of each group, the sharing of information outside the group cannot be monitored. Participants will be informed of this risk prior to consenting to participate.

During the intervention, participants will be asked to join the videoconference platform from a safe/private space (McCarthy et al., 2021) and encouraged against using their full name for confidentiality reasons.

In accordance with the BPS (2021) Code of Human Research Ethics, confidentiality will be breached if participants are at risk of physical or psychological harm, including contacting their next of kin (NOK), GP, or emergency services. Participants will be informed of this prior to consenting to participate.

Coercion and Deception

Individuals will not be pressured into participating. All aims of the study will be provided prior to consenting. Participants will be reminded of their right to withdraw without explanation at the start of each questionnaire and intervention session.

Participant Distress and Burden

Questionnaires will be as short as possible and PPI will inform the accessibility of all supporting documents, reducing the potential for distress/burden from the point of advertisement and throughout.

While there is preliminary evidence of ACT improving mood post-stroke (Graham et al., 2015; Majumdar & Morris, 2019; Ooi & Steverson, 2023; Rauwenhoff et al., 2023; Sathananthan et al., 2022), potential risks will be highlighted during recruitment to improve feelings of preparedness and reduce the likelihood of distress.

Criteria of no severe cognitive impairments or communication difficulties will ensure participants can engage with the demands of the study, keeping distress and burden to a minimum. Excluding those without access to a private space during the intervention will reduce the likelihood of conversations being heard by those not participating and the associated distress this may cause for both participants and bystanders.

To minimise distress and burden during questionnaire completion and the intervention, breaks will be provided/encouraged. Group rules will encourage participants to be mindful of the sensitive nature of topics discussed and therefore how much they share with the group about their personal experiences.

Risk Management

Prior to consenting to participate, contact details for mental health services/charities/helplines will be provided at the end of the information sheet. This information will be re-sent with the questionnaires, during each session and at follow-up.

When assessing eligibility, individuals will be excluded if they have a history of complex mental health difficulties to ensure participants can engage with the content of the questionnaires and intervention. This will reduce the likelihood of sensitive topics of suicide in the group setting, further reducing the potential for participant distress.

As discussed under 'Confidentiality, Anonymity and Data Protection', participants must provide contact details for their NOK and GP at the time of consenting to participate to ensure appropriate steps can be taken if concerns for their wellbeing arise. If risk is identified during the intervention, as well as contacting the above, the individual(s) will be asked to stay on the call to discuss a safety plan. A risk management protocol will be followed.

Debriefing

Participants will have space for reflection in each group session. If risk is identified/disclosed in a session, participants will receive a 1:1 debrief with signposting as appropriate.

A 1:1 debrief will be given to all participants on study completion, outlining the aims/background, procedures taken place and why, and how to seek psychological support.

Analysis

Multiple methods of analysis are chosen to improve understanding and confidence in the results (Lane & Gast, 2014). These are outlined below.

Effect Size

Effect sizes estimate "the magnitude of a relationship", irrespective of sample size (Tarlow & Penland, 2016, p. 228). To assess this, the percentage of non-overlapping data (PND) and percentage of data exceeding the median (PEM) are recommended for SCED's with datasets smaller than 20 (Lenz, 2013).

The PND assesses the degree of change between baseline and intervention phases (Lenz, 2013) and can be easily interpreted due to its visual displays (Ma, 2006). It can be liable to Type II errors due to its focus on single data points (Ma, 2006; Tarlow & Penland, 2016), so Lane and Gast (2014) advise against using the PND alone.

To overcome this, Ma (2006) suggests using PEM which assesses the direction and magnitude of change. Scores range from zero to one (Ma, 2006), and while liable to Type I errors, is recommended in datasets that have outliers and/or variability (Lenz, 2013).

Due to their respective limitations, both the PND and PEM will be conducted to improve the validity and reliability of the analysis.

Visual Analysis (VA)

According to Kennedy (2005), VA is key for a SCED to demonstrate and interpret the effect of an intervention. It enables evaluation of the trend, level and stability of data (Lane & Gast, 2014).

Two types of VA will be conducted: a within-condition analysis assessing the pattern of data within each phase (Lane & Gast, 2014) and a between-condition analysis comparing data between each phase (Kennedy, 2005).

It is recommended that between-condition VA compares median rather than mean scores to minimise the influence of outliers (Lane & Gast, 2014). However, neither VA should be utilised in isolation (Lane & Gast, 2014) emphasising the importance of both for this project.

Reliable Change Index (RCI)

It is recommended that VA should be supported by statistical data analyses where possible (Bouwmeester & Jongerling, 2020; Morley & Adams, 1991). Therefore, RCI will be conducted to understand whether the change observed is significant and reliably exceeds what is expected from measurement error alone (Blampied, 2022; Jacobson & Truax, 1991).

Analyses will monitor changes between pre- and post-intervention scores and will be presented in a modified Brinley (scatter) plot (Blampied, 2022). Recommendations proposed by McAleavey (2024) will be considered.

References

- APA. (2008). Reporting standards for research in psychology: Why do we need them? What might they be? *The American Psychologist*, 63(9), 839.
- Association, S. (2017). *State of the Nation: Stroke Statistics*. <https://www.stroke.org.uk/stroke/statistics>
- Bays, C. L. (2001). Quality of life of stroke survivors: a research synthesis. *Journal of Neuroscience Nursing*, 33(6), 310-316.
- Blampied, N. M. (2022). Reliable change and the reliable change index: still useful after all these years? *The Cognitive Behaviour Therapist*, 15, e50. <https://doi.org/10.1017/S1754470X22000484>
- Bond, F. W., Lloyd, J., Flaxman, P. E., & Archer, R. (2015). Psychological flexibility and ACT at work. *The Wiley handbook of contextual behavioral science*, 459-482. <https://doi.org/10.1002/9781118489857.ch22>
- Bouwmeester, S., & Jongerling, J. (2020). Power of a randomization test in a single case multiple baseline AB design. *PloS one*, 15(2), e0228355. <https://doi.org/10.1371/journal.pone.0228355>
- BPS. (2021, 5th April 2021). *BPS Code of Human Research Ethics*. The British Psychological Society. <https://www.bps.org.uk/guideline/bps-code-human-research-ethics>

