According to Bouwmeester and Jongerling (2020), the MBD holds more power with groups of participants than single cases as outcomes in each phase are averaged. The revised “quality rating scale for [the] Risk of Bias in *N*-of-1 Trials” therefore argues a minimum of five datapoints at baseline (Tate et al., 2013, p. 619). This improves monitoring of the level, trend, and variability of data, which is important if attrition is high (Kratochwill et al., 2010). The baseline length will range from five to seven weeks.

Attrition is problematic when participant dropout causes less than five datapoints at baseline or occurs at a critical timepoint (e.g., during the intervention) (Kratochwill et al., 2010). Attrition at each stage will be reported in a flow chart, as per the Reporting Standards for Research in Psychology (APA, 2008).

The risk of attrition will be mitigated using a two-phase AB design, whereby A is the baseline (control), and B is the intervention (Levin et al., 2021). The longevity of change will be monitored three- and six-months post-intervention, reducing study demands compared to an ABA design where the second A acts as another control (Kazdin, 2021). Six-month follow-ups may occur after thesis submission for the purpose of publication if recruitment presents a challenge.

Participants

Nine adult stroke survivors will be recruited via NHS services (e.g., Early Supported Discharge Stroke Teams, IAPT services) and stroke charities. In SCEDs, six participants are recommended (Kratochwill et al., 2013), though nine will be recruited to account for attrition, with three being assigned to each baseline length (five, six, or seven weeks).

Inclusion

Adults (>18 years) will be included if they have:

- Suffered a stroke over three months ago.
- No other neurological illness.
- Not currently receiving any psychological intervention.
- No severe communication difficulties.
- No severe cognitive impairments.
- No current or historical suicidal ideation/self-harming behaviours.
- Not been diagnosed with major long-term health conditions in the last 12 months (except for stroke or trans-ischaemic attack; TIA).
- Access to a device with a camera, stable internet connection and private space.

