A poster will be circulated via NHS services and stroke charities, containing a link to an online survey (JISC, 2021). Here, participants can view the information sheet, consent form, and eligibility questionnaire. A consent to contact form and researcher contact details will be available should anyone prefer discussing the study before consenting to participate. To ensure accessibility to the study, the consent to contact form can be signed by the individual themselves or, if unable to sign (for example, due to physical impairment following stroke preventing ability to write, or due to healthcare appointments being held remotely), they can provide verbal consent to be contacted by the researcher to their clinician. The clinician can then sign the consent to contact form on their behalf.

Those meeting the inclusion criteria will attend a 30-minute video call to confirm eligibility, including ability to use videoconferencing platforms as per guidance for remote research (McCarthy et al., 2021). Guidance for accessing video calls will be provided.

Once a group is identified, participants will be randomly allocated to a baseline length (five, six or seven weeks) and provided a start date. Visual calendars will mark the dates of

each phase/task. Reminders and links to the questionnaire will also be sent weekly. During baseline and intervention phases, the CompACT-10 (Golijani-Moghaddam et al., 2023) will be completed weekly.

The intervention, delivered by the research team, lasts eight weeks. Each session is two hours, including breaks. Permission to access the protocol for the modifications to the intervention was granted (Large et al., 2019) and has been received. ACT training will be sought for the chief investigator prior to the study commencing.

Participants will have time at the end of each session for group reflections with reminders of where to access mental health support.

Immediately before and after the intervention phase and at three- and six-month follow-ups, participants will complete all questionnaires. At six-months, a 30-minute debrief will be offered.

As per the BPS Code of Human Research Ethics (BPS, 2021), all participants will receive a £10 gift card as reimbursement for their time.

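### PND depends on the number of baseline scores, so the sample-size property stated before it does not carry over to it; the resulting bias is modest but systematic, and it favours shorter or sparser baselines

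*Combined protocol and SAP*

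**What the plan says.** All places are in the combined protocol and SAP.

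- **Effect Size:** the section opens with a cited definition in which effect sizes estimate magnitude "irrespective of sample size". The next sentence names PND and PEM as the means of assessing this in datasets smaller than 20. On PND it says "The PND assesses the degree of change between baseline and intervention phases". It admits one weakness, "It can be liable to Type II errors due to its focus on single data points", advises against using PND alone, and concludes that "both the PND and PEM will be conducted to improve the validity and reliability of the analysis".
- **Design:** "The baseline length will range from five to seven weeks". The section cites a minimum of five baseline datapoints and treats dropout that leaves fewer as a problem.
- **Participants and Procedure:** nine people are randomly allocated, three to each baseline length. CompACT-10 is completed weekly in both phases, and the intervention lasts eight weeks. All questionnaires are also completed just before the intervention. The text does not say whether that form replaces the last weekly one or adds to it.
- **CompACT-10:** higher scores are better.

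The text available gives no adjustment of PND for baseline length, no reference value by length, and no rule for missed weekly forms.

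**The concern.** PND compares each intervention score with the best baseline score. The best of seven scores is on average higher than the best of five, so a longer baseline sets a higher bar for the same benefit. This design varies baseline length on purpose and by randomisation, so expected PND differs between the three groups even when the therapy does exactly the same thing in each.

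The same mechanism rewards incomplete baselines. Removing a baseline score can leave the maximum where it is or lower it, but cannot raise it, so PND can only stay the same or go up. The five-week group starts exactly at the cited minimum and has no spare score.

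At stake is how individual PND values are read in a study whose primary aim is preliminary efficacy. A reader who takes the opening sentence at face value would treat a PND from a seven-week baseline and one from a five-week baseline with a missed form as being on the same scale.

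**Working it through.** **Figure to reproduce.** None. The plan states no effect-size target or expected PND.

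**Inputs from the documents.** Baseline scores n = 5, 6 or 7 (6, 7 or 8 if the pre-intervention form is an extra point); about 8 intervention scores; higher is better.

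**Assumptions.** The documents give no effect size, within-person SD or autocorrelation. The shift d (in within-person SDs) is therefore shown over a range, for normal scores with a level step between phases.

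**Formula.** For independent scores, expected PND = ∫ n·φ(x)·Φ(x)^(n−1)·[1 − Φ(x − d)] dx. With d = 0 this is exactly 1/(n + 1): 1/6, 1/7 and 1/8.

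| d | n = 5 | n = 6 | n = 7 | Gap, 5 minus 7 (rounded figures) |
|---|---|---|---|---|
| 0 | 16.7% | 14.3% | 12.5% | 4.2 |
| 0.5 | 29.3% | 26.1% | 23.6% | 5.7 |
| 1 | 44.9% | 41.4% | 38.5% | 6.4 |
| 1.5 | 61.4% | 58.1% | 55.3% | 6.1 |
| 2 | 75.8% | 73.3% | 71.1% | 4.7 |
| 3 | 93.5% | 92.6% | 91.8% | 1.7 |

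**Extra pre-intervention point.** With 6, 7 or 8 scores, d = 1 gives 41.4%, 38.5% and 36.1%, a gap of 5.3 points.

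**Autocorrelation (simulated).** At d = 1, n = 5, 6, 7 gives 48.2%, 44.6%, 41.6% for lag-1 correlation 0.3, and 54.3%, 50.8%, 47.9% for 0.6. The gaps are 6.6 and 6.4 points, so the pattern holds.

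**PEM (simulated).** At d = 1: 81.1%, 81.8%, 81.8%. The median is not pushed upward by extra points, so PEM is almost unaffected.

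**Missed baseline forms.** These figures take d = 1 and forms missed regardless of score.

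- Five-week baseline: 44.9% with none missed, 49.4% with one, 55.2% with two.
- Seven-week baseline: 38.5%, about 41.4% and 44.9%.
- Losing one form raised an individual's PND in about 14% of simulated five-week series and 9.6% of seven-week series, and lowered it in none. In the seven-week case the rise, when it occurred, averaged about 30 points.

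**Size against noise (d = 1).** The SD of one person's PND is 27.0, 26.2 and 25.4 points for n = 5, 6, 7. One intervention score is worth 100/8 = 12.5 points. With three people per group, the five-week mean exceeded the seven-week mean in 58% of simulations and fell below it in 35%.

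**All-pairs alternative.** This is the share of all baseline–intervention pairs in which the intervention score is higher, with ties as half. For independent scores its expectation is Φ(d/√2). At d = 1 that is Φ(0.707) = 76.0% for any n. With lag-1 correlation ρ, each pair k weeks apart contributes Φ(d/√(2(1 − ρ^k))). Averaging over pairs with 8 intervention scores and ρ = 0.6 gives 77.2% for n = 5 and 76.9% for n = 7.

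**The case against.** The strongest reply has four parts.

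1. **The sentence is a general definition from a cited source.** It can be read as being about magnitude, or about numbers of participants. This largely stands: a reader might infer that the plan asserts PND to be unaffected by baseline length, but it never says so outright. However, the next sentence ties the definition to PND and PEM and speaks of dataset size, and nothing later withdraws the property for PND.

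2. **No harmful use of PND is planned.** A reader might infer that PND will be averaged or compared across baseline groups, mixing the therapy effect with the allocated length. The text available describes no such step, and the aims call the methods idiographic. Allocation is also random with three per length, so averaging would bring in a small fixed offset between groups, not confounding with patient characteristics. This stands.

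3. **The missing-form effect is easily overstated.** A reader might infer that every missed form raises PND, or that whoever has the thinnest baseline gets the best score. Neither follows. An individual's PND rises only if the missing score was the sole maximum and an intervention score lies between it and the next highest. The rise is an average, though it is never offset by falls. The Design section already flags baselines cut below five by dropout, and the patient-involvement section describes reminders.

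4. **The plan already hedges.** It admits PND's reliance on single points and adds PEM, visual analysis and a reliable change index. That helps the overall reading, but it does not correct PND itself. The admitted risk is also of missing an effect, whereas missed baseline forms push towards apparent benefit.

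**Conclusion.** The concern holds for PND alone; it does not extend to both planned effect sizes. For the same true shift, expected PND falls by roughly 2 to 6 points from a five-week to a seven-week baseline over shifts of 0 to 3 SD, and missed baseline forms raise it on average. The direction does not depend on the assumed shift, on autocorrelation up to 0.6, or on whether the pre-intervention form counts as an extra point. The exact sizes rest on assumed normal scores and a level step.

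A reader might infer that this could overturn the study's findings. It would not do so alone: the gap is about a quarter of one person's SD at 1 SD (6.4 against about 26). It still merits correction because it is systematic, tied to the randomised feature of the design, favourable to sparser baseline data, and cheap to remove.

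**What to change.** In the Effect Size section:

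1. Qualify the opening sentence so that independence from sample size is not claimed for PND, and say that PND tends to fall as baseline scores are added.
2. Report beside PND the all-pairs overlap index (ties as half). Its expectation is free of baseline length for independent scores and nearly so under autocorrelation.
3. State the number of completed baseline scores beside each PND, and whether the pre-intervention form is among them.
4. If PND is compared or averaged across participants, add a sensitivity version using the last five completed baseline scores. Where fewer than five exist, the stated count shows it.
5. If 1/(n + 1) is printed as a no-effect reference, label it as holding only for independent, untied scores. At lag-1 correlation 0.6 the no-effect PND is about 27% for four points and 32% for three, not 20% and 25%. Ties push it the other way.

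The cost is a few lines of SAP wording, a little code and one extra statistic per participant. The last-five version ignores one or two early scores in the longer groups (one more in each group if the pre-intervention form is an extra point), in that sensitivity analysis only. Recruitment, data collection and treatment are unchanged.
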